## **I. Background and Significance**

Digital pills provide real-time verification of medication ingestion events and can be used to monitor medication adherence; previous studies have demonstrated their acceptability in real-world patient populations. Digital pills comprise a radiofrequency emitter combined with a standard gelatin capsule that is compounded with a study medication. Upon ingestion of the digital pill, the chloride ion gradient in the stomach energizes the radiofrequency emitter, transmitting a unique signal of medication ingestion that is captured by a wearable Reader. The Reader acts as a relay, storing and transmitting ingestion data to a smartphone and cloud based server. Ingestion data is then available for real time interpretation by clinicians. Digital pill technology has been previously applied to opioid ingestion, diabetes management, and as a surrogate for directly observe therapy in schizophrenics.

Direct measures of medication adherence are an important advance in the study of medication adherence, especially among patients with poor adherence linked to non-alcohol substance abuse. Although recent studies have demonstrated pre-exposure prophylaxis (PrEP) with once daily Truvada is efficacious in preventing HIV infection, protection is highly dependent on adherence. There is a clear dose response relationship between PrEP adherence and prevention of HIV transmission. Post-hoc analyses of the iPrEX data (corroborated by the PROUD and iPERGAY studies) found that individuals whose drug levels were consistent with taking 4 or more doses of TDF/FTC (e.g., Truvada) a week had a greater than 90% level of protection from HIV; but only 50% of MSM in iPrEX achieved consistent adherence. Substance use, especially stimulant use, among MSM occurs syndemically in the context of other mental health vulnerabilities (most notably depression, sexual trauma, and intimate partner violence that increase their risk for condomless anal sex and HIV infection. Similarly, among HIV-infected MSM, the impact of substance use on ART adherence and HIV treatment outcomes is also well established and recent studies have already identified substance use as a significant barrier to optimal PrEP adherence among MSM.

In this study, we plan to develop and deploy a novel smartphone based intervention, PrEPsteps. PrEPsteps, a smartphone-based intervention that addresses real-time PrEP nonadherence among MSM with non-alcohol substance use (MSM+S). PrEPsteps is a brief Cognitive Behavioral Therapy intervention to improve PrEP adherence among MSM+S. It is comprises an established, empirically supported adherence intervention (LifeSteps) augmented for this population by the inclusion of A) app-delivered booster sessions; B) contingent reinforcement/corrective feedback; and C) evidence based Screening, Brief Intervention and Referral to Treatment (SBIRT) addressing non-alcohol substance use. Innovatively, PrEPsteps responds to objective, real-time PrEP adherence data obtained from a digital pill that directly measures TDF/FTC ingestion. I will conduct focus groups among HIV negative MSM+S to inform the specification, presentation and design of PrEPsteps, and test the usability and sustainability of PrEPsteps and the digital pill in a pilot randomized controlled trial (N=60) of MSM+S using PrEP. Finally, we will conduct qualitative interviews to assess the response to PrEPsteps and digital pill in order to further optimize PrEPsteps.

## **II. Specific Aims**

***Aim 1:*** *To inform the specification of the PrEPsteps adherence intervention with participant-generated content solicited through five focus groups. We will solicit feedback from the focus group participants on all the components of the PrEPsteps intervention delivery content and platform.*

***Aim 2:*** *To test, through a pilot randomized controlled trial (N=30x2), the feasibility, acceptability and potential for an effect of PrEPsteps on PrEP adherence, compared to treatment as usual (TAU) in HIV seronegative MSM with non-alcohol substance use who are initiating or continuing PrEP.*

***Aim 3:*** *To assess the acceptability of the PrEPsteps intervention components (and the digital pill) through qualitative exit interviews with those randomized to the PrEPsteps condition.*

## **III. Recruitment**

Eligible participants are HIV-negative cis-gender MSM who have non-alcohol substance use (identified in medical record) and are currently taking PrEP. We will use recruitment techniques previously employed in Fenway studies, including venue outreach (bar, club, cruising areas), community outreach, word of mouth from past or present participants in FCH studies, and advertising (print, clinic flyers and electronic media). Potential participants will also be screened during clinical appointments at Fenway Health by study staff. New patients at Fenway Health are given a Notice of Privacy Practices which informs them that their protected health information may be utilized for research when the research proposal is IRB-approved and conducted in accordance with HIPAA privacy and confidentiality rules. Further, under HIPAA, as employees of the covered entity (Fenway Health), the study staff may utilize medical records to identify potential participants. Potentially eligible patients will be identified using electronic reports from the data team. A study staff member will then work with medical assistants and/or providers before approaching patients to assess interest. After entering the room and prior to screening, the study staff member will explain the study before asking permission to complete the screening questionnaire. Those who appear to be eligible will be invited to participate in the study after their appointment, or set up an appointment in the future.

During periods of remote work (i.e., when in-person recruitment on Fenway Health medical floors is not feasible due to COVID-19-related restrictions), we will additionally run a Tableau report (after securing a HIPAA waiver from Fenway Health IRB), to identify patients who meet basic eligibility criteria. For patients that meet initial eligibility criteria, we will reach out via phone and/or patient portal to those who gave permission to be contacted directly by TFI for research opportunities. For individuals who have not yet opted-in, we will reach out to their provider for permission to contact them. If a provider does not respond to emails, we will attempt to call them or connect with their support staff via email or phone. We will document patients' permission or providers' permission to contact their patients in a password-protected file, which will be saved on Dropbox. Upon receiving permission from providers to contact their patients directly, we will reach out to patients via the patient portal. The initial message will not contain any sensitive information (e.g. mention of PrEP status, HIV status, etc.), and will use the subject line, "Paid Research Study Opportunity." We will respond to general questions about the study (e.g., related to eligibility criteria) directly in the patient portal for the patient's convenience; however, we will not respond to non-study-related questions and will ask participants to contact us directly should they require more information. The portal message will allow patients the option of opting out of future communications from the PrEPsteps study team. If a patient opts out, we will not contact

## Detailed Protocol

### Development of Ingestible Biosensors to Enhance PrEP Adherence in Substance Users (PrEPsteps)

them again, unless they decide to opt back in. If a patient does not opt out within 7 days, we will reach out either via phone or via email with a provider letter. We will abide by patients' stated contact preferences. The provider letter sent via email will not include any sensitive information, and will use the subject line, "Paid Research Study Opportunity." After 7 days or more of no response, we will send an additional communication. We will additionally use Tableau reports to identify HIV-negative individuals who are currently receiving Truvada for PrEP from the Fenway Pharmacy. We will include study flyers in the mailed Truvada prescriptions for these patients, which will contain details about the study, as well as contact information for those interested.

The PrEPsteps study team will also utilize the recruitment database established from the TechPrEP study to recruit potential participants. The recruitment database was created from TechPrEP participants who gave permission to be contacted for future studies, and elected to provide their email address, cell phone number, and/or zip code. The recruitment database is saved as a password-protected Excel file on Dropbox, which the study staff will access to recruit potential participants for PrEPsteps. The staff will contact potential participants who provided a zip code located in or near Boston, MA either via phone or via email. We will abide by potential participants' stated contact preferences.

Our recruitment efforts, in line with our previous recruitment initiatives, will include targeted recruitment of men of color, by adapting our recruitment materials, and conducting recruitment drives in minority communities. Initially, a potential participant will contact study staff, express interest in the study, and provide the staff person with their name and telephone number for future contact. Also, staff will use a study screener on Fenway medical floors that cover inclusion criteria for PrEPsteps (as well as a screener for an investigation recruiting a similar study population, the IMPACT study). The staff will briefly describe the study requirements and procedures for IMPACT and PrEPsteps, and if the prospective participant is interested, an eligibility screening will be conducted for both studies. This recruitment method has been utilized by the recruitment team at Fenway Health for biomedical studies with similar inclusion criteria. Contact information for individuals who were ineligible for or have completed IMPACT, and are interested in enrolling in PrEPsteps, will be stored in a password-protected spreadsheet on a shared folder in the Fenway server accessible only to members of the PrEPsteps study team.

We will advertise aim 2 of the study on social media (e.g., Grindr, Growlr, Facebook, Twitter, Reddit, Instagram, Craigslist) in coordination with the recruitment team at the Fenway Institute. We will also receive referrals for potentially eligible participants through the use of a centralized pre-screener facilitated by the recruitment team and BSRP. Finally, BIDMC will be used as a site for passive recruitment, in which a PowerPoint slide advertising the study will be shared/presented at regular HIV conference meetings attended by BIDMC faculty.

**IV. Subject Selection**

Inclusion Criteria	Exclusion Criteria
Aim 1: 
 
1) Cis-gender MSM with problematic stimulant use (identified in medical record as stimulant dependence or recurrent stimulant use that interferes with daily life: ICD 304, 305 and 292) or self-report (e.g. reported stimulant use in the past 6 months)
 
2) HIV-negative
 
3) On PrEP or qualifies for PrEP
 
4) Age 18 or older
 
	Aim 1: Does not speak English
Aim 2: 
 
1) Cis-gender MSM with moderate to severe non-alcohol substance use disorder (via MINI assessment)
 
2) HIV-negative
 
3) On PrEP or initiating PrEP
 
4) Has qualifying laboratory testing: Cr clearance, HBV, liver function tests
 
5) Owns a smartphone with Android or iOS
 
6) Age 18 or older
 
	Aim 2: 
 
1) Does not speak English
 
2) HIV positive
 
3) History of Crohn's disease or ulcerative colitis
 
4) History of gastric bypass, bowel stricture
 
5) History of GI malignancy or radiation to abdomen
 
6) Unable/unwilling to ingest digital pill
 
7) Allergy to gelatin, silver or zinc (components of the digital pill)
 
8) Does not qualify for PrEP (abnormal liver function, or Cr Clearance <60)
 

Aim 3: Participants in Aim 2 will be enrolled in Aim 3	Aim 3: Did not participate in Aim 2

*Justification for Inclusion Criteria*

MSM represent the largest risk group for new HIV infection nationally (Centers for Disease Control and Prevention, 2015). We did not include women or heterosexual men in the current study because the intervention approach may vary in different communities. Moreover, Fenway's extensive experience working with MSM makes this site most appropriate for the development of an intervention that focuses on MSM. This study proposes to recruit biological MSM. The decision not to recruit transgender men or women is based upon the following considerations. The priority for this treatment development study is to develop a treatment that will identify important relationships between non-alcohol substance use and PrEP nonadherence so that we can modify these experiences to improve adherence in this population. If we are successful in developing PrEPsteps in the MSM population, we will expand our study to explore if the intervention can be translated towards transgender individuals who may have different barriers to PrEP adherence.

*Justification for Substance Use Disorder*

Among MSM enrolled in the iPrEX study, individuals who experience suboptimal and eventual nonadherence had concomitant substance use disorders. While the majority of MSM with PrEP nonadherence in iPrEX were stimulant users, substance use in general has been a predictor of PrEP nonadherence, especially after the end of

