## Detailed Protocol

### Development of Ingestible Biosensors to Enhance PrEP Adherence in Substance Users (PrEPsteps)

the Readers and smartphone app. Additionally, we will solicit methods to prepare potential participants for using digital pills in PrEP adherence monitoring.

Next, we will conduct five focus groups that will explore the structure of PrEPsteps. The focus groups will start with a general description of PrEPsteps. Next we will discuss each component of PrEPsteps: the LifeSteps framework, contingent reinforcement/corrective feedback (CR/CF) and SBIRT interventions. Iterative refinements to the structure of PrEPsteps, the wording of messages in CR/CF and content within SBIRT interventions. We will additionally inform the design features that improve the acceptability of each component of PrEPsteps: the timing of delivered interventions, how many messages are delivered daily, and the design and appropriate display of messages on the smartphone interface.

We will compile important themes in digital pill presentation, preparing participants for digital pill investigations, the structure and delivery of PrEPsteps and content of PrEPsteps into a final product package of digital pill hardware, smartphone app interface and interventions that comprise PrEPsteps. We will present this package to one final focus group (N=10) to ensure that all components are acceptable and understandable by potential study participants. Once this final focus group is complete, we will program PrEPsteps with our industry partner, ectectRx, into the smartphone app and conduct a series of pilot tests in response to mock episodes of adherence and nonadherence to ensure the technology functions and correct components of PrEPsteps are displayed in response to detected ingestion patterns.

**Aim 2 and 3:** In Aims 2 and 3, we will deploy PrEPsteps in a pilot randomized controlled trial in MSM with non-alcohol substance use who are on PrEP. This portion of the study will involve 7 study visits (most of them remote) over the course of 6 months where participant ingest digital pill PrEP daily. Details of the PrEPSteps intervention, delivery of intervention and all study visits are described below:

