**Study Visit 2:** Procedures for this visit will be conducted onsite at Fenway Health, or partially remote, if necessary, in response to COVID-19. This visit will take place 2 weeks after Study Visit 1. We will contact participants on day 7 to remind participants of their appointment. Participants will be randomized into the control arm (treatment as usual with digital pills to measure adherence) or the intervention arm (PrEPsteps). Randomization will occur via a predetermined schema using REDCap. We will review the previous 2 weeks of adherence data and reconcile discordant or nonadherent events with participants. At this study visit and subsequent study visits, participants will have the option of viewing the original digital pill training videos used in Study Visit 1 as a refresher course for technology training if they desire. Participants will return any unused digital pills from the prior 14-day period (to be counted by study staff), and will additionally undergo a blood draw for dried blood spot (DBS) testing for tenofovir diphosphate (to measure adherence and compare DBS against the digital pill). For all participants, a 30-day supply of Truvada digital pills will be dispensed at this study visit. We will contact participants via text message on days 16, 19, 21 to ensure technology is functioning. *This contact schema (i.e., reminder messages for study visit) will remain the same for each subsequent visit.*

In the event that Study Visit 2 is conducted in a partially remote format, we will randomize the participant, review the previous 2 weeks of adherence data, and provide the link to the digital pill training videos during the virtual (Zoom) portion of this visit. All remaining study visit procedures will be conducted during the onsite portion of this visit. If necessary, the 30-day supply of digital pills may be mailed to participants if they are unable to attend the in-person portion of the visit due to COVID-19.

Arm	Study Visit 2 Procedures
-----	--------------------------

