## VII. Biostatistical Analysis

**Aim 1:** We will conduct qualitative analysis on individual interviews in aim 1 to elucidate themes of technology acceptance, design, and optimal timing and delivery of messaging.

**Aim 2:** We will calculate descriptive statistics regarding the degree of adherence collected from the digital pill. We will also calculate the accuracy of the digital pill in comparison to pill counts and validate ingestion data compared to DBS. We additionally will report overall percent adherence and measure the association between percent adherence and PrEPSteps. Additionally we will report weeks of adherence ( $>4$  doses a week) and measure the association between weeks of adherence and the use of PrEPSteps. Because this is a pilot, proof-of-concept study, we will not be powered to determine the degree of adherence the use of a digital pill alone confers upon study participants.

**Aim 3:** We will conduct an applied thematic analysis on all recorded interviews using NVivo 12.

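### Aim 2 admits men starting PrEP and men already taking it, but neither the described allocation nor the two arm comparisons use this status; if adherence differs between the groups, the pilot estimate loses some precision.

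*Combined protocol and SAP*

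**What the plan says.** **Who is enrolled.** Section IV, Aim 2 inclusion criterion 3, admits men "On PrEP or initiating PrEP". Aim 2 in Section II likewise covers men "who are initiating or continuing PrEP". The Screening Visit text has a laboratory provision that mentions initiators.

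Other places describe only men already using PrEP. Section I refers to a "pilot randomized controlled trial (N=60) of MSM+S using PrEP". Section III describes eligible men as "identified in medical record) and are currently taking PrEP". The introduction to Aims 2 and 3 in Section VI places the trial "in MSM with non-alcohol substance use who are on PrEP".

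**Allocation.** Under Study Visit 2: "Randomization will occur via a predetermined schema using REDCap". No stratification factor, block size or minimisation is described.

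**Analysis.** For Aim 2, Section VII will "measure the association between percent adherence and PrEPSteps" and will do the same for weeks of adherence. It names no model, covariate or subgroup.

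The second copy of the protocol in the file reads the same on each of these points.

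**The concern.** The outcome is adherence to a daily drug. For an initiator, the 14-day run-in is his first fortnight on that drug; for a continuing user, it samples a habit already formed. PrEP status at entry is therefore a plausible prognostic factor. The eligibility rule itself creates it, and it is settled before anyone is randomised.

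With 30 men per arm and no stratification on this status, the arms can easily differ in their share of initiators. If the groups adhere differently, that imbalance is part of the observed arm difference. Leaving the factor in the error term also gives a wider interval than necessary. These are two views of a single cost: lost precision in the one estimate from which Aim 2 is to judge whether PrEPsteps might work.

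**Working it through.** **The plan's own figure.** Aim 2 is a "pilot randomized controlled trial (N=30x2", and 30 × 2 = 60 agrees with the total in Section I. The plan gives no alpha, power, effect size or SD, so the sample size cannot be reproduced from design inputs.

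**Inputs.**
- From the documents: n = 30 per arm, N = 60.
- Assumed, because the documents give no values: initiator share p = 10%, 30% or 50%; adherence gap between initiators and continuing users g = 10, 20 or 30 percentage points; SD of percent adherence s = 25 points (20 and 30 as sensitivity).

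**Step 1: how large is chance imbalance?** With K = 60p initiators split at random between two arms of 30, the number x in one arm is hypergeometric. The difference in initiator share is (2x − K)/30, with SD = (2/30) × √[30 × p(1−p) × 30/59].

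| Share p | K | SD of imbalance (points) | P(≥10 points) | P(≥20 points) |
|---|---|---|---|---|
| 10% | 6 | 7.8 | 0.20 | 0.02 |
| 30% | 18 | 11.9 | 0.40 | 0.16 |
| 50% | 30 | 13.0 | 0.44 | 0.20 |

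**Step 2: what does imbalance do to the arm difference?** Shift = imbalance × g. A 20-point imbalance moves the difference in percent adherence by 0.20 × 10 = 2, 0.20 × 20 = 4 or 0.20 × 30 = 6 points. With g = 20, a one-SD imbalance moves it by 1.6, 2.4 or 2.6 points at p = 10%, 30% or 50%.

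**Step 3: unadjusted precision.** SE = s√(2/30) = 25 × 0.2582 = 6.45. The 95% half-width is 1.96 × 6.45 = 12.65, or 12.7 points.

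**Step 4: precision after adjustment.** R² = p(1−p)g²/s². The half-width becomes about 12.65 × √(1−R²), and the equivalent total N is 60/(1−R²).

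| g | p | R² | Half-width (points) | Equivalent N |
|---|---|---|---|---|
| 10 | 10% | 0.014 | 12.6 | 60.9 |
| 10 | 30% | 0.034 | 12.4 | 62.1 |
| 10 | 50% | 0.040 | 12.4 | 62.5 |
| 20 | 10% | 0.058 | 12.3 | 63.7 |
| 20 | 30% | 0.134 | 11.8 | 69.3 |
| 20 | 50% | 0.160 | 11.6 | 71.4 |
| 30 | 10% | 0.130 | 11.8 | 68.9 |
| 30 | 30% | 0.302 | 10.6 | 86.0 |
| 30 | 50% | 0.360 | 10.1 | 93.8 |

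**Sensitivity to the SD, at g = 20.** With s = 20, R² is 0.09, 0.21 and 0.25, and equivalent N is 65.9, 75.9 and 80.0. With s = 30, R² is 0.04, 0.093 and 0.111, and equivalent N is 62.5, 66.2 and 67.5.

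**Step 5: comparison with run-in adherence.** Every participant has 14 days of digital-pill data before allocation. If run-in adherence correlates with the outcome at r (also not given), adjusting for it multiplies the SE by √(1−r²): 0.954, 0.866 or 0.714 for r = 0.3, 0.5 or 0.7. For PrEP status at g = 20, s = 25 and p = 50%, the factor is √0.84 = 0.917. The figures in Step 4 are marginal, so the gain from PrEP status on top of run-in adherence could be smaller and cannot be derived from the documents.

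All of these figures concern percent adherence. The same reasoning applies to weeks of adherence, but no size was calculated for it.

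**The case against.** Several points stand.

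- **No bias.** A reader might infer that mixing the groups biases the PrEPsteps estimate. It does not: randomisation keeps the unadjusted estimate unbiased on average, and a valid unadjusted interval already allows for chance imbalance.
- **Prognostic value is assumed.** The documents do not say that initiators and continuing users differ in adherence; the predictor they stress is substance use. With no gap there is nothing to gain.
- **The initiator share may be low.** Three sections describe current users, and one recruitment route puts flyers in Truvada prescriptions mailed by the Fenway Pharmacy. At a 10% share, a 20-point imbalance has a probability of only about 2%.
- **Silence is not exclusion.** It is tempting to read the plan as committing to an unadjusted analysis and an unstratified list. Section VII states no model of either kind, and the REDCap schema is undescribed and could already be stratified.
- **Recording is not shown.** At screening, labs are drawn for initiators and also for anyone without qualifying results, so the draw does not itself identify initiators. No dedicated status field is described.

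The pilot label does not remove the point. The power disclaimer in Section VII concerns what a digital pill alone confers, not the arm comparison, and chance imbalance matters most in small trials. Prespecifying the covariate also prevents the choice from being made after an imbalance is seen.

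**Conclusion.** The point holds as a modest, inexpensive improvement in precision and interpretability. As written, the plan uses a status settled before randomisation in neither the allocation nor the two comparisons. Under a 20-point gap and an SD of 25, adjustment is worth the equivalent of about 4, 9 or 11 extra participants at shares of 10%, 30% or 50%. With a 10-point gap it is worth between 1 and 3. Larger gains need a large gap together with a substantial initiator share, and nothing in the documents establishes either.

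The documents do not support calling the unadjusted result biased or the trial invalid. The point also depends on initiators actually being enrolled, which the sections leave in conflict.

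**What to change.** 1. In Section VII, prespecify initiating versus continuing PrEP at screening as a covariate in both the percent-adherence and the weeks-of-adherence comparison, alongside 14-day run-in adherence if that is also adjusted for. Section VII names no model, so the sentence must name one for each outcome.
2. Reconcile Section I, Section III and the introduction to Aims 2 and 3 in Section VI (men already using PrEP) with Section II, Section IV and the Screening Visit text (initiators included). If only current users are enrolled, the covariate is not needed.
3. Describe the REDCap schema. Stratify it by PrEP status only if randomisation is still open and it is not already stratified this way. The Study Visit 1 text shows that enrolment was under way around September 2022, so this step may have little reach; the covariate alone is enough.

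The cost is one model degree of freedom out of 60 − 2 = 58, with no new visits or measurements, provided the status is held as a field at screening. If it is not, that field must be added or completed from screening records.
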